8.4.3 REPORTING UNANTICIPATED PROBLEMS TO PARTICIPANTS

The PI and study team will follow DSMB guidance regarding reporting of unanticipated problems to participants.

9 STATISTICAL CONSIDERATIONS

We will post or pre-register our planned analysis plan in clinicaltrials.gov. Information will be provided on the analysis plan for the primary endpoint.

9.1 STATISTICAL HYPOTHESES

[Primary endpoint] Our primary hypothesis is that patients randomized to the Somryst treatment will experience a greater improvement (from baseline) in the Insomnia Severity Index (ISI) at post-intervention (9 weeks) compared to those randomized to mEUC, and scores will continue to be better

18 May 2022

than mEUC patients at 6 months post-intervention. The null hypothesis is that there will be no difference in the ISI scores between patients randomized to the Somryst treatment versus those assigned mEUC.

[Secondary endpoints] Our secondary hypothesis is that Somryst will result in greater improvement in quality of life, as captured by the more general SF-12 that will be assessed pre- and post-intervention in both the Somryst and mEUC participants. We will use the validated method of Brazier et al. to calculate utilities (QALY penalties) from baseline and post-intervention (9 weeks) SF-12 data by first mapping responses to the simpler SF-6D scale and then using a regression model to estimate single index scores.^{92, 108} Additionally patients in the Somryst treatment will exhibit greater improvement in scores for self-reported daytime sleepiness, satisfaction with care, actigraphy-assessed sleep duration and actigraphy-assessed sleep efficiency, and self-reported sleep quality compared to mEUC patients.

9.2 SAMPLE SIZE DETERMINATION

Prior studies suggest that CBT-I yields approximately an 8-point reduction in the ISI, our primary measure of insomnia, with the standard deviation (SD) of post-intervention change scores being 4 to 5 points. Our expectation is that the improvement in patients assigned to the intervention condition (Somryst) will be 8 points or greater, and that those assigned to minimally enhanced usual care (mEUC) will exhibit a 5-point improvement. Typically, we expect the SD of change scores to increase for longer intervals (e.g., 6 or 12 months), and have therefore conservatively based our power calculations on a SD (change) of 6.0. Accordingly, randomization of 200 patients to Somryst versus mEUC (1-to-1 ratio) will provide 90% power to detect a differential reduction (post-intervention and 6-month follow-up) in ISI of 3 points or larger, using a 2-tailed Wald chi-square test of the appropriate contrast. This sample size estimate allows for up to 15% attrition, such that we have baseline data on all 200 patients (collected prior to randomization), but follow-up data on only 170.

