9.4.2 ANALYSIS OF THE PRIMARY ENDPOINT(S)

Mixed-model RM-ANOVA will be used to estimate and compare the changes in the primary endpoint (ISI) and other patient-important outcomes (e.g., insomnia symptom severity, daytime sleepiness) between Somryst and mEUC. The RM-ANOVA model will include Group (Somryst versus mEUC), Time (baseline, post-intervention and 6-month follow-up), and the Group × Time interaction as fixed factors with an unstructured residuals covariance matrix. This will yield estimates of the within-group means and standard errors at each assessment. Specific interaction contrasts (e.g., Group × Pre-vs-Post Intervention) will be estimated to estimate the magnitude and test the statistical significance of the differential change in insomnia symptoms using the Wald χ^2 statistic. We will plot the mean insomnia scores across assessments, stratified by treatment group, to elucidate the nature of the interaction (i.e., whether Somryst resulted in significantly greater improvements [or lesser worsening] than mEUC). If, despite randomization, the two groups differ substantially (p<0.10 after stepdown Bonferroni correction) on one or more sociodemographic or clinical factors assessed at baseline, sensitivity analyses will be performed in which these factors are included as covariates in the RM-ANOVA, in order to rule out the possibility that the results from the primary analyses are attributable to group differences on these factors. The same analyses will be repeated to estimate and compare changes in the primary endpoint and secondary endpoints between Somryst and mEUC at 6-months.

Significance will be evaluated with a two-tailed p value of 0.05. To control for multiplicity, postintervention will be evaluated first and if significant timepoints post-intervention and 6-months followup will be evaluated. In addition, estimated marginal means \pm 95% confidence intervals will be calculated for each assessment point and Cohen's d will be used as an estimate of effect size for the change from baseline to each assessment point.

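### The 90% power in Section 9.2 is per contrast: it holds at 9 weeks, but power to claim the 6-month effect under the Section 9.4.2 testing order is about 82–87% at SD 6.0, or 88–90% at the plan's expected 9-week SD

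*Combined protocol and SAP*

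**What the plan says.** Section 9.2 (Sample Size Determination) expects an 8-point improvement on Somryst and says that "those assigned to minimally enhanced usual care (mEUC) will exhibit a 5-point improvement", a difference of 3 points. It reports prior studies "with the standard deviation (SD) of post-intervention change scores being 4 to 5 points". Because it expects the SD to grow over longer intervals, the investigators "have therefore conservatively based our power calculations on a SD (change) of 6.0". With 200 randomized 1:1 and up to 15% attrition, leaving 170 with follow-up, the design "will provide 90% power to detect a differential reduction (post-intervention and 6-month follow-up) in ISI of 3 points or larger". The calculation refers to one contrast only: "using a 2-tailed Wald chi-square test of the appropriate contrast".

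Section 9.4.2 (Analysis of the Primary Endpoint(s)) sets the level: "Significance will be evaluated with a two-tailed p value of 0.05". It then sets the order: "To control for multiplicity, postintervention will be evaluated first and if significant timepoints post-intervention and 6-months followup will be evaluated".

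The table in Section 3 names ISI change to 9 weeks and to 6 months as the primary endpoints, and the primary hypothesis in Section 9.1 covers both. Section 9.2 mentions neither the testing order nor a joint power, and gives no correlation between the two contrasts.

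**The concern.** Section 9.2 attaches one power figure to both time points, although the testing rule treats them differently. The 9-week contrast is tested first at the full 0.05, so its power is the ordinary single-test figure. The 6-month contrast can support a claim only if the 9-week contrast has also succeeded. The probability of that claim therefore cannot exceed the power of either contrast alone, and it falls below both unless the two test statistics are very highly correlated or the 9-week test is nearly certain to succeed.

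At stake is the accuracy of the planning statement for a named primary endpoint. A reader of Section 9.2 would take the chance of establishing a 6-month effect, if it is truly 3 points, to be 90%. Under the plan's own rule it may be lower, by an amount that depends on two quantities that Section 9.2 does not tie to this claim: the SD at 9 weeks and the correlation between the contrasts.

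**Working it through.** **Inputs.** From Section 9.2: difference 3 points at both visits; planning SD of change 6.0; 9-week SD from prior studies 4 to 5; 170 evaluable, taken as 85 per arm. From Section 9.4.2: two-sided 0.05, 9 weeks first, then 6 months. Assumed, because the documents do not give it: correlation ρ between the two test statistics, shown from 0 to 0.9.

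**Step 1: reproduce the stated figure.**
- SE = 6 × √(2/85) = 0.920.
- Power = Φ(3/0.920 − 1.96) = Φ(1.30) = 0.903. A noncentral t calculation gives 0.900.
- In reverse, 90% power needs 85 per arm, and 170/0.85 = 200 randomized.

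The 90% is therefore the power of a single contrast tested without any precondition.

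**Step 2: 9-week test.** It comes first at the full 0.05, so its power is 0.903 at SD 6.0. At SD 5 it is Φ(3/0.767 − 1.96) = 0.9745, and at SD 4 it is Φ(3/0.614 − 1.96) = 0.9983.

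**Step 3: 6-month claim under the sequence.** Power = P(Z₉wk > 1.96 and Z₆mo > 1.96), from a bivariate normal with correlation ρ, 85 per arm at both visits, and SD 6.0 at 6 months:

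| SD at 9 weeks | ρ = 0 | ρ = 0.5 | ρ = 0.7 | ρ = 0.9 |
|---|---|---|---|---|
| 6.0 | 0.8157 | 0.8372 | 0.8512 | 0.8727 |
| 5 | 0.8801 | 0.8888 | 0.8947 | 0.9016 |
| 4 | 0.9016 | 0.9025 | 0.9030 | 0.9031 |

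At ρ = 0 the entries are simple products, for example 0.9031 × 0.9031 = 0.816 and 0.9745 × 0.9031 = 0.880. Simulation of the first row gave 0.816, 0.837 and 0.852 at ρ = 0, 0.5 and 0.7.

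**Step 4: a reference value for ρ.** Both changes subtract the same baseline. If the three visits had equal variances σ² and equal pairwise correlations r (an assumption), the covariance of the two changes would be σ²(1 − r) and each variance 2σ²(1 − r), so ρ = 0.5. That gives 83.7% with SD 6.0 at both visits and 88.9% with SD 5 then 6.0.

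**Step 5: attrition.** If nobody were lost by 9 weeks (assumed 100 per arm, then 85 at 6 months, SD 6.0 at both), the power to claim 6 months would be 85.1% to 89.3% for ρ from 0 to 0.9.

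**Step 6: power of the 6-month test once it is reached.** This is joint power divided by 9-week power. At SD 6.0 for both visits: 0.8157/0.9031 = 0.903 (ρ = 0), 0.8372/0.9031 = 0.927 (ρ = 0.5), 0.8727/0.9031 = 0.966 (ρ = 0.9). At SD 5 then 6.0: 0.8801/0.9745 = 0.903 (ρ = 0) to 0.9016/0.9745 = 0.925 (ρ = 0.9).

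**The case against.** The strongest reply is that no stated number is wrong. Section 9.2 refers to a test of one contrast, its figure reproduces for one contrast, and it never claims 90% for succeeding on both. This stands: the gap lies in what the figure is attached to, not in how it was computed.

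The second reply is that the larger shortfall needs SD 6.0 at 9 weeks, whereas Section 9.2 expects 4 to 5 there and adopted 6.0 with longer intervals in mind. This also stands, and it limits the shortfall to between 0 and about 2 points on the plan's expected SDs. It does not remove the point, because Section 9.2 bases its power calculations on 6.0, names both visits, and does not say that a smaller SD was used for 9 weeks.

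Third, ρ = 0 is an unlikely extreme for two changes that share a baseline in the same patients, and attrition is given as a maximum. Both are fair, and are why a range is shown.

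Three stronger readings are tempting but unsupported:
- *The 9-week effect also lacks 90% power.* It does not: it is tested first at the full 0.05 and keeps 90.3%.
- *The trial is too small.* Holding 90% for the 6-month claim at SD 6.0 throughout would need, for example, 101 evaluable per arm (238 randomized) at ρ = 0.5. The plan makes no explicit promise of joint power, and at its own 9-week SDs 200 comes within about 2 points.
- *A missed 6-month result would be wrongly read as no sustained effect because its power was below 90%.* Step 6 shows that once the 9-week test is won, the 6-month test has at least 90.3% power under the plan's assumptions. The loss comes from 9-week failures, after which 6 months is not tested at all.

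Finally, the Section 9.4.2 sentence is awkwardly worded, and I could not check it against Figure 2 in Section 9.4.3. The sequential reading is the natural one, and the calculation depends on it.

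**Conclusion.** The concern holds as a reporting gap confined to the 6-month claim. Section 9.2's 90% is correct per contrast and applies in full to 9 weeks. It overstates the probability of claiming a 6-month effect under the Section 9.4.2 order: about 82–87% if SD 6.0 applies at both visits, and about 88–90% if the 9-week SD is 4 to 5. Against the 90.3% for a single contrast, the shortfall is about 3 to 9 points in the first case and 0 to about 2 in the second.

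These figures assume a true 3-point difference at both visits, 85 evaluable per arm at each, a normal approximation to the Wald test, and ρ between 0 and 0.9. The correlation is the input that the documents do not supply. The 9-week SD matters most: at SD 4 the shortfall all but disappears whatever the correlation.

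**What to change.** In Section 9.2, label the 90% as the power of a single contrast, say that it holds for the 9-week test, and add the power for the 6-month claim with its assumptions. For example:

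> With 85 evaluable patients per arm, a 3-point difference and an SD of change of 6.0, power is about 90% for each contrast taken alone, and this applies to the 9-week test. Because 6 months is tested only after a significant 9-week result, power to claim a 6-month effect is about 82–87% if the SD is 6.0 at both visits, and about 88–90% if the 9-week SD is 4 to 5, for an assumed correlation between the contrasts of 0 to 0.9.

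The cost is two sentences and a slightly less favourable stated figure for 6 months. The sample size, the significance level, the testing order and the analysis model stay as they are.

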9.3 POPULATIONS FOR ANALYSES

All primary analyses will be conducted according to the intent-to-treat principle, with all randomized patients included in the analysis and their group classification (Somryst versus minimally EUC) based on the condition to which they were randomly assigned.

9.4 STATISTICAL ANALYSES

9.4.1 GENERAL APPROACH

The distributions of all clinical measures will be reviewed for outliers. Those exhibiting substantial skewness will be transformed (e.g., log or square root) to make their distribution more appropriate for parametric procedures. Independent-sample t-tests and chi-square analyses will be used to examine baseline differences between the two treatment groups (Somryst vs. mEUC) in clinical and

sociodemographic characteristics. All primary analyses will be conducted according to the intent-to-treat principle, with all randomized patients included in the analysis and their group classification (Somryst versus mEUC) based on the condition to which they were randomly assigned.

9.4.2 ANALYSIS OF THE PRIMARY ENDPOINT(S)

Mixed-model RM-ANOVA will be used to estimate and compare the changes in the primary endpoint (ISI) and other patient-important outcomes (e.g., insomnia symptom severity, daytime sleepiness) between Somryst and mEUC. The RM-ANOVA model will include Group (Somryst versus mEUC), Time (baseline, post-intervention and 6-month follow-up), and the Group × Time interaction as fixed factors with an unstructured residuals covariance matrix. This will yield estimates of the within-group means and standard errors at each assessment. Specific interaction contrasts (e.g., Group × Pre-vs-Post Intervention) will be estimated to estimate the magnitude and test the statistical significance of the differential change in insomnia symptoms using the Wald χ^2 statistic. We will plot the mean insomnia scores across assessments, stratified by treatment group, to elucidate the nature of the interaction (i.e., whether Somryst resulted in significantly greater improvements [or lesser worsening] than mEUC). If, despite randomization, the two groups differ substantially (p<0.10 after stepdown Bonferroni correction) on one or more sociodemographic or clinical factors assessed at baseline, sensitivity analyses will be performed in which these factors are included as covariates in the RM-ANOVA, in order to rule out the possibility that the results from the primary analyses are attributable to group differences on these factors. The same analyses will be repeated to estimate and compare changes in the primary endpoint and secondary endpoints between Somryst and mEUC at 6-months.

Significance will be evaluated with a two-tailed p value of 0.05. To control for multiplicity, postintervention will be evaluated first and if significant timepoints post-intervention and 6-months followup will be evaluated. In addition, estimated marginal means \pm 95% confidence intervals will be calculated for each assessment point and Cohen's d will be used as an estimate of effect size for the change from baseline to each assessment point.

Missing Data: We will use multilevel mixed models to perform intent-to-treat RM-ANOVA. There will be no missing data at baseline, because we will only randomize patients who have successfully completed the baseline assessment, and therefore all 200 patients will be included in the analyses. The software used to estimate the mixed models yields full-information maximum-likelihood parameter estimates that are robust with respect to data that are "missing at random". This will appropriately handle the possibility that attrition (or missing data) is related to either baseline level of the outcome measure, group assignment, or their interaction. However, if we discover that attrition is associated with some other characteristic (e.g., sex or age), we will use multiple imputation (chained equation approach^{104, 105}) and include the associated characteristic in the imputation model.¹⁰⁶ We will do everything possible to collect data on the reasons for dropout, who decided the participant should drop out (e.g., their PCP), and whether the dropout involves any aspect of participation in the study. Even if the patient drops out of the intervention, we will still seek to collect their key outcome information. We will compare key characteristics of participants with and without missing data. In cases where there are large differences

18 May 2022

in missing data, we will cautiously interpret our findings and will consider limitations in generalizability that might have been introduced by these differences.

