5 STUDY POPULATION

5.1 INCLUSION CRITERIA

In order to be eligible to participate in this study, an individual must meet all of the following criteria:

- 1. Provision of signed and dated informed screening consent form
- Stated willingness to comply with all study procedures and lifestyle considerations (see Section 5.3, Lifestyle Considerations) and availability for the duration of the study (8 months)
- 3. Males and females; Age 18-65
- 4. Adults with moderate insomnia symptoms as documented on initial eligibility screen based on validated cut-off for community samples (Insomnia Severity Index Score >10)
- 5. Willingness to adhere to the digital therapeutic treatment (study-app based intervention) or enhanced usual care study regimen
- 6. Be Spanish-speaking or bilingual (English and Spanish) adults
- 7. Self-identify as Hispanic or Latinx
- 8. Report experience of sleep disturbances for at least 3x/week
- 9. Report experience of sleep disturbances for at least 3 months

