6.3 MEASURES TO MINIMIZE BIAS: RANDOMIZATION AND BLINDING

Randomization. After completing the baseline assessment, patients will be randomly assigned in a 1:1 ratio to either the Culturally Adapted Somryst or minimally Enhanced Usual Care (mEUC) condition. Randomization will be generated by a computerized random-number sequence programmed by the study statistician and implemented in the secure, password-protected, encrypted data tracking program. The sequence will be unknown to research assistants enrolling patients.

Blinding. One research staff member (TBN) will be responsible for randomizing participants and so this research assistant and the PI will be unblinded to study condition. Participants will also be unblinded to study condition since treatment conditions will be obvious to them. Research assistants conducting the post-intervention (9 weeks) and 6-month outcome assessments will be blinded to participants' treatment condition, as this is preferred to minimize risk of bias in outcome ascertainment.

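### The primary mixed model leaves baseline ISI free to differ by arm; constraining it to be equal adds 0 to about 6 power points under assumed correlations and needs no new data

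*Combined protocol and SAP*

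**What the plan says.** Section 9.4.2 specifies the primary model: "The RM-ANOVA model will include Group (Somryst versus mEUC), Time (baseline, post-intervention and 6-month follow-up"), and Group × Time, with unstructured covariance. The test comes from this model: "Specific interaction contrasts (e.g., Group × Pre-vs-Post Intervention) will be estimated". Baseline ISI is therefore one of three outcome levels, and the Group term lets its mean differ by arm.

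Baseline factors are adjusted for only if the arms differ at p<0.10 after a step-down Bonferroni correction. In that case "sensitivity analyses will be performed in which these factors are included as covariates in the RM-ANOVA". Whether covariate × Time terms are included is not stated.

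Section 6.3 fixes the order of events: "After completing the baseline assessment, patients will be randomly assigned in a 1:1 ratio". The missing-data part of section 9.4.2 adds that "we will only randomize patients who have successfully completed the baseline assessment, and therefore all 200 patients will be included in the analyses".

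Section 9.2 bases power on change scores. It cites prior work "with the standard deviation (SD) of post-intervention change scores being 4 to 5 points", and the authors "have therefore conservatively based our power calculations on a SD (change) of 6.0".

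**The concern.** Because baseline precedes randomization, any baseline ISI difference between the arms is due to chance. The planned model still estimates that difference and subtracts it in full. When the slope of follow-up on baseline is below 1, full subtraction over-corrects: the estimate moves by (1 − slope) times the chance imbalance, and the standard error is larger than it need be. This concerns efficiency. It is not a bias or a sample-size error.

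The covariate analysis raises a separate point. It is meant to show that the result does not come from baseline differences. A covariate entered only as a main effect shifts all time points equally, so in complete data it drops out of a change contrast. The adjusted result would then match the primary one by construction and could be mistaken for reassurance.

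**Working it through.** **Inputs from the documents.** Difference 3 ISI points, SD(change) 6, 200 randomized 1:1, 15% attrition (85 of 100 per arm followed), two-sided 0.05 (sections 9.2 and 9.4.2). Baseline is complete and collected before randomization (sections 6.3 and 9.4.2).

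**Assumed.** Baseline SD s0, follow-up SD s1 and their correlation ρ, because the documents give none of these. SD(change) is held at 6 throughout.

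**The plan's own figure.** 3/(6·√(2/85)) − 1.96 = 3.26 − 1.96 = 1.30, which gives 90.3%. The stated 90% reproduces.

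**Variances.** Let b = ρ·s1/s0 be the slope and r² = s1²(1 − ρ²) the residual variance. With maximum likelihood, 100 baselines and 85 follow-ups per arm:

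- Planned model: 2[r²/85 + (1 − b)²s0²/100]
- Equal baseline means: 2r²/85

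The constraint removes the second term, so asymptotically it cannot lose precision. As a check on the algebra, r² + (1 − b)²s0² equals the variance of change, 36. With complete data the planned contrast is exactly the difference in mean change.

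**Worked example, s0 = s1 = 6, ρ = 0.5.** b = 0.5, r² = 27, (1 − b)²s0² = 9.

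- Planned: 2(27/85 + 9/100) = 0.815, SE 0.903; 3/0.903 − 1.96 = 1.36, power 91.3%.
- Constrained: 2·27/85 = 0.635, SE 0.797; 3/0.797 − 1.96 = 1.80, power 96.4%.

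| s0, s1 | ρ | b | Variance, planned → constrained | Ratio | Power, planned → constrained |
|---|---|---|---|---|---|
| equal | 0.3 | 0.30 | 0.803 → 0.551 | 0.69 | 91.8 → 98.1% |
| equal | 0.5 | 0.50 | 0.815 → 0.635 | 0.78 | 91.3 → 96.4% |
| equal | 0.7 | 0.70 | 0.828 → 0.720 | 0.87 | 90.9 → 94.2% |
| s1 = 1.5·s0 | 0.3 | 0.45 | 0.831 → 0.738 | 0.89 | 90.8 → 93.7% |
| s1 = 1.5·s0 | 0.5 | 0.75 | 0.843 → 0.817 | 0.97 | 90.5 → 91.3% |
| s1 = 1.5·s0 | 0.7 | 1.05 | 0.847 → 0.845 | 1.00 | 90.3 → 90.4% |
| 4, 6 | 0.33 | 0.50 | 0.833 → 0.753 | 0.90 | 90.8 → 93.3% |

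The last row allows for a narrower spread at baseline than at follow-up, which is plausible given entry at "Insomnia Severity Index Score >10". At ρ = 0 with equal SDs the gain would be 7.2 points, so about 6 applies for ρ of roughly 0.3 or more.

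**Smaller SD(change).** At 5, the top of the plan's cited range, planned power is already 97.5–98.0% and the gain is at most about 2 points for ρ of 0.3 or more. At 4, planned power is 99.8% and there is essentially nothing to gain.

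**Checks.** A three-time-point information-matrix calculation (equal SDs, 15% with baseline only) agrees with the equal-SD rows. Simulation (20,000 runs, 15% dropout) gave 91.6 → 96.3% at equal SDs and ρ = 0.5, and 90.8 → 93.3% for SDs 4 and 6. Rejection under the null was 5.2–5.5% for both models (10,000 runs), so both are valid.

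**Size of the chance shift, s0 = 4 and b = 0.5.** SD of the imbalance: 4·√(2/100) = 0.566. Shift: SD 0.5·0.566 = 0.283, mean absolute value 0.283·√(2/π) = 0.23 points (about 8% of the 3-point target), 95% within ±0.55, in either direction. At slope 1 it is zero.

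**Covariate terms.** In one simulated complete three-wave data set, the planned contrast was −3.217. It stayed at −3.217 with the covariate as a main effect and became −3.298 with covariate × Time. With 15% dropout in further simulated sets, the main-effect version moved the contrast by at most 0.02, against 0.03 to 0.20 with covariate × Time.

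**The case against.** The planned contrast estimates the declared endpoint, change from baseline. It matches the sample-size basis, is unbiased over randomizations and meets its power. On this view, preferring another valid model is optional, and the headline gain depends on assumed correlations and the deliberately cautious SD of 6. With SDs 4 and 6, the 95% interval half-width falls only from 1.96·√0.833 = 1.79 to 1.96·√0.753 = 1.70 points. The entry cut-off also applies at the screen, while the schedule of activities lists a separate baseline ISI, so baseline scores are not directly truncated.

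These points are fair and limit the claim to efficiency. Three more stand in part:

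- The chance shift and the power gain are one effect. The shift variance, 0.283² = 0.08, is exactly the removed term 2·0.25·16/100 = 0.08. They should not be counted as two benefits.
- The plan does not say that covariates enter as main effects only. The accurate criticism is that the form is unspecified, and that the simplest reading gives an analysis that cannot do its job.
- The change has a small cost. The model would report one common baseline mean, so the arm-specific baseline summaries promised in section 9.4.2 would have to be descriptive. Section 9 also promises to post or pre-register the analysis plan, so a posted version may need updating.

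None of this argues against the constraint itself, which randomization after baseline justifies.

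**Conclusion.** The point holds as an efficiency improvement that should be made. The planned test is valid and adequately powered under its own assumptions. Constraining the baseline means gives an estimate at least as precise asymptotically: variance ratio 0.69 to 1.00 over the scenarios shown, or 0 to about 6 power points at SD(change) 6. The ratio depends on ρ and on s1/s0, not on SD(change), so the interval can narrow even where power is already near its ceiling. All of these sizes rest on assumed correlations and SDs.

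The unspecified covariate form is a smaller, separate weakness of the sensitivity analysis. It does not depend on the assumed correlation.

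**What to change.** Keep the mixed model, the three time points, the unstructured covariance and the order of testing with 9 weeks first. Replace the free Group effect at baseline with a common baseline mean, and let Group effects enter at 9 weeks and 6 months. All 200 randomized patients stay in the model. A follow-up-only model with baseline ISI × Time gives essentially the same estimate but drops patients with no follow-up score, so the constrained form is preferable. Use it also for secondary outcomes that have a pre-randomization baseline, and report observed baseline means by arm descriptively.

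Replace the p<0.10 trigger with one prespecified adjusted sensitivity model that names its covariates and includes covariate × Time terms. The study team has to choose the covariates.

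The cost is SAP wording, a line of model code, a small change to the baseline reporting and an update of any posted analysis plan, all before unblinding. No new data, visits or patients are needed.

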9.4.4 SAFETY ANALYSES N/A

9.4.5 BASELINE DESCRIPTIVE STATISTICS

18 May 2022

Independent-sample t-tests and chi-square analyses will be used to examine baseline differences between the two treatment groups (Somryst vs. mEUC) in clinical and sociodemographic characteristics.

9.4.6 PLANNED INTERIM ANALYSES N/A.

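### The baseline-imbalance sensitivity analysis names no covariate × Time term, so on its plain reading it returns essentially the unadjusted treatment contrast

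*Combined protocol and SAP*

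**What the plan says.** Section 9.4.2 of the combined protocol and SAP fits a repeated-measures model to ISI at baseline, 9 weeks and 6 months. Its terms are Group, Time and "the Group × Time interaction as fixed factors with an unstructured residuals covariance matrix". The treatment effect is read from change contrasts: "Specific interaction contrasts (e.g., Group × Pre-vs-Post Intervention) will be estimated".

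Baseline imbalance is handled in the same section. If the arms differ on any sociodemographic or clinical factor at "p<0.10 after stepdown Bonferroni correction", then "sensitivity analyses will be performed in which these factors are included as covariates in the RM-ANOVA". The declared aim of this step is to show that the primary finding does not stem from such imbalances. The text does not say whether a factor enters as a main effect or with its interaction with Time. The same analyses are repeated for the secondary endpoints and at 6 months. Sections 9.4.1 and 9.4.5 supply the screening tests: "Independent-sample t-tests and chi-square analyses will be used to examine baseline differences".

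**The concern.** Baseline ISI is one of the three responses, so the treatment effect is a difference in change. A factor measured once and added as a plain covariate moves all three of a patient's expected scores by the same amount. It can explain why one arm scores higher throughout, but not why one arm improves more. Improvement is what the contrast measures.

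The adjusted and unadjusted results would then agree whether or not the factor had distorted the comparison. A report could present that agreement as evidence that imbalance does not explain the effect, when no effective adjustment had been made.

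**Working it through.** **Inputs from the plan.** Section 9.2: 200 randomized 1:1, 170 with follow-up (15% attrition), SD of change 6.0, target difference 3 points, 90% power. Section 9.4.2: the model above, two-sided 0.05, full-information maximum likelihood, no missing baseline data.

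**1. The plan's own figure.** SE = 6 × √(2/85) = 0.920. Power = Φ(3/0.920 − 1.96) = Φ(1.30) = 0.903, and 170/0.85 = 200. The stated 90% reproduces and is not in dispute.

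**2. Algebra, complete data.** Let x be the factor and b its main-effect slope. The adjusted mean in arm g at time t is Ȳ(g,t) − b·(x̄(g) − x̄). Subtracting the baseline mean of the same arm gives Ȳ(g,t) − Ȳ(g,0). The term in b cancels for any b, so the estimate is unchanged.

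The SE is unchanged too. With unstructured covariance, the likelihood splits into (i) the density of the two change scores and (ii) the density of baseline ISI given those changes. The slope b appears only in (ii), and the two parts share no parameters. With covariate × Time, x enters (i), and the change scores are adjusted.

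**3. One complete simulated data set (100 per arm).** The 9-week contrast is −2.33251 without the covariate and −2.33251 with its main effect. The SE is the same in both models: 0.82400 under ML and 0.82815 under REML. Covariate × Time moves the estimate to −1.73.

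**4. Repeated simulation.** Assumptions not in the documents: true effect −3, imbalance 0.4 SD, covariate shifting ISI change by 2 points per SD. Expected confounding is 0.4 × 2 = 0.8 points. On average 15% are missing at 6 months, about half of them also at 9 weeks. Each row below is the mean 9-week estimate over 150 data sets. In setting A the covariate has no effect on baseline ISI. In setting B it raises baseline ISI by 2 points per SD.

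| Data | No covariate | Main effect | Covariate × Time |
|---|---|---|---|
| Complete, A | −3.786 | −3.786 | −2.994 |
| Complete, B | −3.900 | −3.900 | −3.101 |
| Random dropout, A | −3.766 | −3.766 | −2.962 |
| Random dropout, B | −3.731 | −3.730 | −2.924 |
| Dropout by covariate, same in both arms, A | −3.676 | −3.685 | −2.904 |
| Dropout by covariate, same in both arms, B | −3.787 | −3.783 | −2.999 |
| Dropout by covariate, opposite by arm, A | −3.505 | −3.582 | −2.945 |
| Dropout by covariate, opposite by arm, B | −3.701 | −3.648 | −3.007 |

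- For random or same-direction dropout, the mean shift from the main effect is about 0.01 points or less at either visit. The largest single-trial shift is 0.17.
- For opposite-direction dropout, the mean shift is 0.05 to 0.08 at 9 weeks and 0.09 to 0.12 at 6 months. The largest single-trial shift is 0.30. In setting A the shift is away from the true −3.
- The unadjusted 9-week SE with attrition is about 0.86 to 0.87.

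A separate check used heavier assumed loss (15% at 9 weeks, about 19% at 6 months), a 0.5 SD imbalance and 12 data sets. The main effect moved the contrast by at most 0.06, and covariate × Time by about 0.89.

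**5. What could be left in the contrast.** Assume a factor correlating 0.3 with ISI change: 0.3 × 6 = 1.8 points per SD.

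- At 0.40 SD imbalance: 0.40 × 1.8 = 0.72 points, or 24% of the 3-point target.
- At 0.5 SD: 0.5 × 1.8 = 0.9 points, or 30%.

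**6. The trigger.** The first step-down threshold for K factors is 0.10/K. With 100 per arm, the standardized difference needed is z × √(2/100).

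- K = 5: 2.326 × 0.1414 = 0.33 SD.
- K = 20: 2.807 × 0.1414 = 0.40 SD.

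The plan does not list the factors, so K is assumed. The procedure holds the family-wise error at 10%, so under valid randomization at least one factor is flagged in at most about 10% of trials.

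**The case against.** The text never says main effects and does not forbid covariate × Time. A statistician working from the stated purpose could add the interaction without contradicting the plan. That is fair: a reader might infer that the plan prescribes main effects, and the documents do not support that. But section 9.4.2 spells out the one interaction it wants and gives none for the covariates, so main effects is the plain reading, and the term that decides whether the check works is left unspecified.

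A reader might also infer that the covariate can never move the contrast. That is exact only with complete data. The plan expects attrition, and under maximum likelihood patients with only a baseline score let a little of the covariate effect through. The movement is small and leaves most or all of the confounding in place.

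Other parts of the plan look at the same factors. Section 9.4.7 repeats the primary analysis within strata of age, gender, comorbidity, depression, anxiety and others. Section 9.4.9 excludes sleep-medication users. It would therefore be wrong to say that an imbalance must go unnoticed. None of these gives an overall adjusted estimate, though, and the multiple imputation in section 9.4.2 concerns attrition.

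Finally, large imbalances are rare. With 100 per arm, 0.5 SD is z = 0.5/0.1414 = 3.54. Over repeated randomizations the primary contrast is not biased by chance imbalance, so the figures in step 5 are conditional on an unlucky draw. This stands, and it limits the weight of the point.

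**Conclusion.** The point holds for the sensitivity analysis as plainly read. A baseline factor added without its interaction with Time leaves the Group × Time contrast and its SE exactly unchanged with complete data. With the planned 15% attrition they are almost unchanged: about 0.01 points on average, up to about 0.12 in the least favourable dropout pattern simulated, against an SE of about 0.86. The analysis cannot exclude baseline differences as an explanation, and agreement with the primary result would say nothing about robustness.

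The invariance is algebraic. The attrition results rest on the simulated dropout patterns. The residual distortion (about 0.7 points at 0.40 SD, 0.9 at 0.5 SD) rests on an assumed correlation of 0.3 and is not a forecast for this trial.

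A reader might infer that the primary test, alpha or sample size is at fault, or that adjustment would raise the trial's power. Neither follows. The defect lies in a conditional sensitivity analysis, and covariates placed there do not alter the primary test.

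**What to change.** In section 9.4.2, state that each baseline factor enters the sensitivity model together with its interaction with Time. An ANCOVA-type alternative also works: model the 9-week and 6-month scores, with baseline ISI and the factors as covariates.

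Add that baseline ISI is not to be a covariate while it is also a response. With slope 1 it would fit the baseline response perfectly, the residual variance would go to zero and the likelihood would be unbounded.

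Preferably, run this analysis in every case for a short pre-specified list of prognostic factors already collected (for example age, sex, baseline sleep-medication use, PHQ-8 and GAD-7), and not only when the step-down trigger fires. The trigger selects on significance, not on prognostic value. Without it, the baseline tests in sections 9.4.1 and 9.4.5 are no longer needed for this purpose and a descriptive table is enough.

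The cost is SAP wording and about 2 further df per covariate, since Time has three levels. No new data or patients are needed.
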